## 4.1.3 Screening

The Screening Period is 4 weeks (28 days). Along with the reports confirming the subject's primary diagnosis of EoE, the Investigator will assess eligibility criteria (see Section 4.2.1 and Section 4.2.2) of the subject based on Screening results. The Global EoE score must be >3 for the subject to continue in the study.

The EGD procedures to determine eligibility (see Inclusion Criterion #7: have evidence of EoE, as defined by ≥15 PEAK eosinophils/HPF. In order to ensure that a diagnosis can be made, at least 5-6 biopsies should be taken including both proximal and distal specimens [~3 each]) will be completed during the Screening Period and the biopsies must be received by the central pathologist by the times noted in this inclusion criterion. EGD must be performed prior to Visit 2 (4-week Baseline Symptom Assessment).

ACTH stimulation test must also be performed prior to Visit 2 (4-week Baseline Symptom Assessment).

With Medical Monitor approval, a subject may be rescreened once if the previous reason for screen failure is no longer present or the subject withdrew due to personal or family reasons that have since resolved. If a subject is rescreened, a new informed consent form (ICF) will be signed and assigned a new number. All tests and assessments must be repeated. However, if the subject is being rescreened for reasons other than the esophagogastroduodenoscopy (EGD), then the EGD does not have to be repeated at rescreening, if the screening EGD occurred within the previous 6 weeks. Each subject will be reviewed and discussed on a case-by-case basis by the Medical Monitors on the study.

#### 4.1.4 4-week Baseline Symptom Assessment (Placebo Run-in)

To enter this phase, subjects must:

• Meet all inclusion criteria that are possible to assess prior to the 4-week Baseline Symptom Assessment including the Global EoE score >3 (Inclusion Criterion #5; EoE score must remain >3 at each of Visits 1, 2 and 3 before randomization, or the subject will be considered a screen failure) except those to be assessed during the 4-week Baseline Symptom Assessment: Inclusion Criterion #7: evidence of EoE as defined by ≥15 PEAK eosinophils/HPF; Inclusion Criterion #8: in the daily diary, report episodes of dysphagia ≥3 days per 7 days during the last 14 days of the 4-week Baseline Symptom Assessment; Inclusion Criterion #9: completion of the daily diary on at least 5 out of each 7 days during the last 14 days of the Baseline Symptom Assessment;

Meet no exclusion criteria that will be assessed prior to the 4-week Baseline Symptom
Assessment (i.e., all except Exclusion Criteria #24: a serum cortisol level <16 μg/dL
(440 nmol/L) at 60 minutes with adrenocorticotropic hormone [ACTH] stimulation test
using 250 μg cosyntropin administered intramuscularly [i.e., an abnormal result on the
ACTH stimulation test]). The ACTH stimulation test should have been completed before
entry into the 4-week Baseline Symptom Assessment, however the results of the test may
be pending.

The subject will complete a site visit at the beginning of the 4-week Baseline Symptom Assessment to complete procedures and assessments noted in Table 4-1.

During the 4-week Baseline Symptom Assessment, baseline symptom severity will be determined and the ability of the subject to be compliant with diary entries will be assessed. Pathology for EGD biopsies may also be assessed (or earlier if possible).

#### 4.1.5 Randomization

## 4.1.5.1 Confirmation of Eligibility

To be eligible for randomization, subjects must satisfy all inclusion/exclusion criteria, including the following inclusion criteria that are expected to be confirmed during the 4-week Baseline Symptom Assessment: Inclusion Criterion #7: evidence of EoE as defined by  $\geq 15$  PEAK eosinophils/HPF; Inclusion Criterion #8: in the daily diary, report episodes of dysphagia  $\geq 3$  days per 7 days during the last 14 days of the 4-week Baseline Symptom Assessment; Inclusion Criterion #9: completion of the daily diary on at least 5 out of each 7 days during the last 14 days of the Baseline Symptom Assessment and Exclusion Criteria #24: a serum cortisol level <16  $\mu$ g/dL (440 nmol/L) at 60 minutes with adrenocorticotropic hormone (ACTH) stimulation test using 250  $\mu$ g cosyntropin administered intramuscularly (i.e., an abnormal result on the ACTH stimulation test). The ACTH stimulation test should have been completed before entry into the 4-week Baseline Symptom Assessment, however the results of the test may be pending.

If the Investigator confirms eligibility criteria are met, he or she will randomize the subject using the Interactive Web Response System (IWRS). The IWRS will confirm the eligibility of the subject pertaining to histology (i.e., confirm histological evidence of the EoE diagnosis as per Inclusion Criterion #7: evidence of EoE as defined by ≥15 PEAK eosinophils/HPF), and provide the randomization number to the Investigator and the Sponsor.

#### 4.1.5.2 Randomization Scheme

A total of 100 adult subjects will be randomized to 1 of 4 doses of APT-1011 (1.5 mg HS, 1.5 mg BID, 3 mg HS, and 3 mg BID) or placebo. Subjects in the HS treatment groups will receive placebo 30 minutes after breakfast in order to maintain the blind.

Randomization will occur in a double-blind manner using an integrated IWRS, and will be stratified by the presence or absence of a history of or current esophageal stricture at Screening and history of a prior positive steroid response to any corticosteroid treatment previously received to treat the subject's EoE captured with demography. Randomization for subjects in Part 1 will be stratified by use, such that a comparable percentage of subjects during the study will be allocated to each of the 5 dosing groups.

#### 4.1.6 Treatment

Figure 4-1 provides an overview of the treatment each subject will receive is determined throughout FLUTE (based on responder status). Symptom improvement or deterioration will be assessed on an ongoing basis.

[figure not shown]

Figure 4-1 Study Schematic

Abbreviations: BID = twice daily; EGD = esophagogastroduodenoscopy; EREFs = Eosinophilic Esophagitis Endoscopic Reference Score; HS = hora somni (before sleep); PGI-C = Patient Global Impression of Change; PGI-S = Patient Global Impression of Severity; PRO = Patient Reported Outcomes; Wk = Week.

## 4.1.6.1 Part 1: Induction (Day 1 to Week 14)

During Part 1, subjects will receive their randomized treatment for 14 weeks.

At Week 12, the subjects will undergo a response assessment, including EGD to assess endoscopic and histologic status. The process overview in Section 6.2 will be followed to determine responder status (as defined in Section 4.1.1) and inform the site thereof. Symptoms will also be assessed. The 14 days prior to Week 12 will be compared to the 14 days prior to Randomization.

Histologic responders and non-responders (at Week 12) will enter Part 2 (see Section 4.1.6.2).

#### 4.1.6.2 Part 2: Maintenance (Week 14 to Week 52)

In Part 2, all subjects classified as histologic responders at Week 12 will continue to be treated according to the dosing group to which they were randomized for Part 1. Subjects may continue on this dose for up to 9 months after the completion of Part 1.

Subjects who are histologic non-responders (see Section 4.1.1) at Week 12 will receive single-blind 3 mg BID in Part 2.

At Week 26, subjects will undergo an EGD with biopsy, to assess histologic response. The process overview in Section 6.2 will be followed to determine responder status (as defined in Section 4.1.1) and inform the site thereof. Symptoms will also be assessed. All subjects classified as histologic responders will continue to be treated according to the dosing group to which they were randomized for Part 1 up to Week 52. The 14 days prior to Week 26 will be compared to the 14 days prior to Randomization.

Subjects who are histologic non-responders (see Section 4.1.1) at Week 26 will stop treatment at Week 28 and enter the 2-week follow-up period and exit the study.

Subjects who complete the study at Week 52 will undergo a response assessment, including EGD to assess endoscopic and histologic status. The process overview in Section 6.2 will be followed to determine responder status (as defined in Section 4.1.1) and inform the site thereof. Symptoms will also be assessed. The subject will be treated with study drug through completion of the EGD associated with the Week 52 visit. The 14 days prior to Week 52 will be compared to the 14 days prior to Randomization.

Subjects will complete a Follow-up Visit 2 weeks after the final dose of study drug (see Section 4.1.8).

#### 4.1.7 Early Termination Procedures

Reasons for early termination are discussed in Section 4.2.3.

APT-1011

The subject should be seen at the site within 7 days of determination of the need to discontinue. If this is not possible due to an SAE or other unforeseen circumstance, it may be completed with a phone visit with the subject or a family member. The eCRF should document why the subject was not available for an on-site visit.

If the subject withdraws consent, the date of and the reason for withdrawing consent only will be collected. Otherwise, the Investigator will make all reasonable effort to complete as much as possible of the procedures for the Early Termination Visit.

The Investigator must complete the eCRF up to the time study drug is terminated (and follow-up, if applicable).

## 4.1.8 Follow-up Visit

Subjects will complete a Follow-up Visit for 1 or more of the following reasons:

- Subject with histologic non-response at Week 26 including subjects on single-blind 3 mg BID;
- Subject completed treatment at Week 52 (following EGD);
- Subject experienced an AE requiring early discontinuation, including food impaction requiring EGD;
- Subjects with worsening symptoms who voluntarily withdraw during the study or who withdraw for any reason.

The Follow-up Visit will occur 2 weeks after the subject takes the final dose of study drug.

All subjects must have a final EGD within 3 weeks prior to completing the Follow-up Visit unless the subject withdraws consent or has a contraindication to EGD.

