<sup>a Data and samples collected for Week 28 in the Part 1 Schedule of Events will also apply for this visit in the Part 2 Schedule of Events in Table 4-3 (as applicable) and procedures will not be repeated. At Week 26 subjects who are histologic non-responders will stop treatment at Week 28 and enter the 2- week Follow-up period. Histologic responders continue on the same dose.

<sup>b The reason for an unscheduled visit will guide procedures, at the discretion of the Investigator.

<sup>c The subject should be seen at the site within 7 days of determination of the need to discontinue. If this is not possible due to an SAE or other unforeseen circumstance, it may be completed with a phone visit with the subject or a family member. The eCRF should document why the subject was not available for an on-site visit.

<sup>d Physical examination will include assessments of weight, general appearance, head and neck, eyes and ears, nose and throat, chest, lungs, heart, abdomen, extremities and joints, lymph nodes, skin, and neurological examination.

<sup>e Vital signs to be collected include pulse, respiratory rate, temperature (°C; after a 5-minute rest in sitting position), and blood pressure (measured from the same arm throughout the study).

<sup>f To be drawn 0700 to 0800 hours, or as close to that window as possible. Subjects must be fasting for an 8 hour period prior to the serum cortisol assessments. Blood may be drawn for serum cortisol (morning fasting) ±3 days of scheduled visit to accommodate accurate timing. If desired, other blood draws scheduled for the visit may be done at the same time. If an ACTH test is scheduled for the visit, the serum cortisol assessment should occur at the same time. The pre-ACTH cortisol level can serve as the baseline serum cortisol level.

<sup>g If abnormal serum cortisol level is reported at the last on-treatment visit for a subject, additional monitoring and ACTH test may be required (see Section 6.3.4).

Adare Pharmaceuticals SP-1011-002

APT-1011

47

- 1) Any time a subject has a morning serum cortisol level  $\leq 5 \mu g/dL$  (138 nmol/L) (confirmed by 2 blood draws)
- 2) Any time a subject reports symptoms of hypercorticism (Appendix 6).

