<sup>h It is expected that the EGD will typically be performed during a separate time from other procedures for a given time point. Both EGD and any other procedures indicated for a study visit must be completed within the window for that study visit. For Screening, the EGD must be completed after the ICF is signed and ≥2 weeks before the date of expected randomization.

<sup>1 During the EGD, the endoscopist will complete the EREFs and ~3 biopsies will be obtained from both the proximal and the distal esophagus (total of 5-6 biopsies). The pathologist will assess histology.

If the subject is discontinuation from the study due to lack of efficacy or other reasons, the Investigator may perform an EGD, if clinically indicated.

<sup>k A 250 μg ACTH simulation test will be performed (at an unscheduled visit) to assess for HPA axis suppression of potential clinical concern as follows:

<sup>1 Subjects who discontinue from the study due to evidence of HPA axis suppression will undergo a 250 μg ACTH stimulation test at the Early Termination Visit. m For the Early Termination Visit, the Investigator should record any occurrence of AEs (14 ± 5 days after discontinuation). Subjects discontinued for HPA issues should be followed until resolution.

<sup>n Only if visit is related to EoE change in symptoms.

Table 4-3 Schedule of Events (Part 2 and Follow-up Visit)

Assessments and Procedures	VISIT								
	Visit 11 (Week 28)	Visit 12 (Week 36)		isit 13 eek 44)	Visit 14 (Week 52) (Response Assessment)	Unscheduled Visit a	Early Termination Visit b	Follow- up Visit	
	196 + 2	252 ± 2	3	08 ± 2	364 ± 2			2 weeks after last dose of study drug	
Histologic responders at Week 26 °	X								
Responder status					X				
Concomitant medication(s)	X	X	X		X	X	X	X	
Physical examination d		X		X	X	X	X	X	
Vital signs e	X	X		X	X	X	X	X	
Chemistry and hematology		X	X	X	X	X	X		
Serum cortisol (morning fasting) f	X	X	X		X g	Optional	X	X	
Urinalysis		X	X	X	X	X	X		
12-lead ECG				X		X	X		
EGD (with EREFs), including collection of multiple esophageal biopsies to be assessed histologically h,i				X k	X	X j			
Urine pregnancy test for women of childbearing potential	X	X	X		X	Optional	X	X	
ACTH stimulation test (250 μg)					X	Optional k	Optional 		
AEs	X	X	X	X	X	X m			

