Global EoE Symptom Score	X	X	X		X	Optional	X		
7-day EEsAI				X		X			
PGIC	X	X	X		X	Optional	X		
PGIS	X	X	X		X	Optional n	X		

Assessments and Procedures	VISIT								
	Visit 11 (Week 28)	Visit 12 (Week 36)	Visit 13 (Week 44)		Visit 14 (Week 52) (Response Assessment)	Unscheduled Visit a	Early Termination Visit b	Follow- up Visit	
			DAY						
	196 + 2	252 ± 2	308 ± 2		364 ± 2			2 weeks after last dose of study drug	
EoE-QoL-A				X		X			
Daily diary	X	X	X	X	X	X			
Study drug dispensed	X (if needed for dosing group change)	X	X						
Drug return and accountability and study drug compliance assessment	X	X	X	X		X	X		
Reason for discontinuation						X			

Abbreviations: ACTH = adrenocorticotropic hormone; AE = adverse event; ECG = electrocardiogram; eCRF = electronic case report form; EEsAI = Eosinophilic Esophagitis Activity Index; EGD = esophagogastroduodenoscopy; EoE = eosinophilic esophagitis; EoE-QoL-A = Adult Eosinophilic Esophagitis Quality of Life Questionnaire; EREFs = Eosinophilic Esophagitis Endoscopic Reference Score; HPA = hypothalamic-pituitary-adrenal; PGIC = Patient Global Impression of Change; PGIS = Patient Global Impression of Severity; SAE = serious adverse event.

<sup>a The reason for an unscheduled visit will guide procedures, at the discretion of the Investigator.

<sup>b The subject should be seen at the site within 7 days of determination of the need to discontinue. If this is not possible due to an SAE or other unforeseen circumstance, it may be completed with a phone visit with the subject or a family member. The eCRF should document why the subject was not available for an on-site visit.

<sup>c Histologic responders will continue on the same dose. Histologic non-responders at Week 26 will stop treatment at Week 28 and enter the 2-week follow-up period.

<sup>d Physical examination will include assessments of weight, general appearance, head and neck, eyes and ears, nose and throat, chest, lungs, heart, abdomen, extremities and joints, lymph nodes, skin, and neurological examination.

<sup>eVital signs to be collected include pulse, respiratory rate, temperature (°C; after a 5-minute rest in sitting position), and blood pressure (measured from the same arm throughout the study).

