# **4.2.3** Early Termination of Subjects

Subjects have the right to discontinue from FLUTE at any time for any reason without penalty or prejudice. The Investigator also has the right to discontinue subjects from the study if he or she feels it is in the best interest of the subject or if the subject is uncooperative or noncompliant.

Should a subject decide to discontinue, all efforts will be made to complete all the early discontinuation procedures as thoroughly as possible.

Subjects who discontinue following prestudy evaluations (i.e., screening procedures and during the 4-week Baseline Symptom Assessment), but before receiving any study drug will be considered screen failures. Only data pertaining to Screening and the reason for screen failure will be included in the database. No additional data will be collected from the time of consent withdrawal

The following reasons for discontinuation will be considered for FLUTE:

- Female subject becomes pregnant;
- Violation of inclusion/exclusion criteria and the Sponsor requires the subject to discontinue;
- Subject withdraws consent and/or chooses to discontinue participation for personal reasons;
- Subject chooses to discontinue, or is discontinued by the Investigator or the Sponsor, due to an AE;
- Subject participates in Part 2 and is classified as a histologic non-responder at Week 26 (see Section 4.1.1).
- Subject uses a prohibited medication (see Section 5.8.1) and the Sponsor requires subject to discontinue;
- In the Investigator or Sponsor's judgment, discontinuation from the study is in the subject's best interest (e.g., SAE [dependent on Investigator clinical judgment], an immediate medical or surgical procedure is required that would compromise the subject's continued participation, intercurrent illness that compromises participation, lack of adequate therapeutic response as outlined in the protocol [relapse; see discussion in Section 4.1.6], or unacceptable risk);
  - Subjects who are discontinued due to lack of efficacy will receive treatment as per Section 5.9.
- Subject is uncooperative or does not comply with protocol requirements (e.g., failure to return for scheduled visits, failure to complete study evaluation tools, failure to return study drug, etc.).
  - Failure or inability to comply with EGD requirements are included in this reason for discontinuation.
  - o This may also include serious protocol violation(s).

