Subjects for whom an AE(s) associated with HPA axis suppression are reported are not required to be discontinued. The Investigator must consult with the Sponsor to discuss and receive approval for any such subjects to continue in the study following the AE(s) associated with HPA axis suppression.

All reasonable efforts must be made to contact subjects who fail to return for scheduled visits and to encourage them to comply with all the procedures. All attempts to contact subjects either by phone, courier, and/or email must be clearly documented.

For any subject who discontinues, procedures to be completed are described in Section 4.1.7.

Subjects who are discontinued from the study will not be replaced.

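### The 3-week limit on the final EGD does not fit Week 26 histologic non-responders, whose last scheduled EGD is nominally 28 days before the Follow-up Visit

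*Protocol*

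**What the plan says.** Protocol Section 4.1.8 and the Follow-up Visit paragraph of the Synopsis set the rule: "All subjects must have a final EGD within 3 weeks prior to completing the Follow-up Visit". Only withdrawn consent and a contraindication to EGD are exempt. The first reason for a Follow-up Visit listed in 4.1.8 is histologic non-response at Week 26, so this group is plainly within the rule. The same section places the visit 2 weeks after the final dose and gives no window.

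The exit route for this group is consistent across the protocol. Under Section 4.1.6.2, histologic non-responders "at Week 26 will stop treatment at Week 28 and enter the 2-week follow-up period and exit the study". Footnote a to Table 4-2 agrees: "At Week 26 subjects who are histologic non-responders will stop treatment at Week 28". So does footnote c to Table 4-3: "Histologic non-responders at Week 26 will stop treatment at Week 28 and enter the 2-week follow-up period".

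Table 4-2 puts the Week 26 visit at Day 182 ± 2 and the Week 28 visit at Day 196 ± 2. It marks an EGD at Week 26 and in the Unscheduled and Early Termination columns, but none at Week 28. The EGD cannot drift later to close the gap, because a footnote requires: "Both EGD and any other procedures indicated for a study visit must be completed within the window for that study visit".

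**The concern.** The 3-week limit suits Week 52 completers. Under Section 4.1.6.2 they are dosed until the Week 52 EGD is done, so Follow-up comes about 14 days after it. Week 26 non-responders stay on drug for another two weeks after their EGD and then wait two more weeks for Follow-up. Four weeks do not fit inside three.

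A site that follows both instructions must add a second endoscopy, with the 5-6 biopsies that Section 6.2.1.1 calls for, in a subject whose non-response is already documented. A site that does not add it has a deviation built in by the calendar. What is at stake is an avoidable invasive procedure or a routine deviation, together with unclear instructions to sites.

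**Working it through.** **Inputs**

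- Limit from final EGD to Follow-up: 3 weeks = 21 days (4.1.8).
- Week 26 EGD: Day 182, window Day 180 to 184 (Table 4-2, with the footnote that holds the EGD inside its visit window).
- Last dose at Week 28: Day 196, window Day 194 to 198 (Table 4-2). Table 4-3 prints the same visit as 196 + 2, that is Day 196 to 198.
- Follow-up: last dose + 14 days (4.1.8).

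**Formula:** gap = (last-dose day + 14) − EGD day.

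| Case | Calculation | Gap (days) | Over 21 by |
|---|---|---|---|
| Nominal | 196 + 14 − 182 | 28 | 7 |
| Shortest, Week 28 as ± 2 | 194 + 14 − 184 | 24 | 3 |
| Longest | 198 + 14 − 180 | 32 | 11 |
| Shortest, Week 28 as + 2 only | 196 + 14 − 184 | 26 | 5 |

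The 21-day limit is not met anywhere in the stated windows. Put the other way, the Week 26 EGD would qualify only if the last dose came no more than 21 − 14 = 7 days after it. That is Day 189 for an EGD on Day 182, and Day 191 for the latest permitted EGD on Day 184. The Week 28 visit cannot be earlier than Day 194.

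**When a repeat EGD would comply.** With Follow-up on Day 210, the qualifying interval runs from 210 − 21 = Day 189 to Day 210. That is 189 − 182 = 7 to 210 − 182 = 28 days after the Week 26 EGD, and 196 − 182 = 14 days if done at the Week 28 visit. The shortest possible interval within the windows is (208 − 21) − 184 = 3 days.

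**Sensitivity to a Follow-up window.** The protocol states none, so these are assumptions.

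- Follow-up at 14 ± 2 days: from 194 + 12 − 184 = 22 to 198 + 16 − 180 = 34 days. The limit is still missed.
- Follow-up at 14 ± 5 days, borrowing the adverse-event recording window from the Early Termination footnotes, which does not define this visit: from 194 + 9 − 184 = 19 to 198 + 19 − 180 = 37 days. Compliance is possible only at favourable extremes. With the EGD and stop on their nominal days, the earliest Follow-up still gives 196 + 9 − 182 = 23 days.

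**Comparison.** For a Week 52 completer whose last dose is on the EGD day, the gap is 14 days, so the limit is met.

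**The case against.** The strongest reply is that the rule can be followed. Section 4.1.8 itself orders the EGD, and Table 4-2 has Unscheduled and Early Termination columns in which to perform and record one. Any repeat from Day 189 to Day 210 complies nominally, and at the Week 28 visit it would come 14 days after the first. This stands: a reader might infer that the protocol asks for something impossible, and it does not. What remains is that neither Section 4.1.6.2 nor the scheduled visits provide for the repeat, and its value is doubtful when non-response has just been shown.

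A second reply is that a subject could comply if Follow-up were early. This also stands in part. Missing the limit in every case depends on Follow-up at exactly 14 days.

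A reader might also infer a contradiction specific to this group between an obligatory and an optional EGD. Section 4.2.3 lists among the reasons for discontinuation "Subject participates in Part 2 and is classified as a histologic non-responder at Week 26" and adds "For any subject who discontinues, procedures to be completed are described in Section 4.1.7". The Early Termination footnote then says that for discontinuation "due to lack of efficacy or other reasons, the Investigator may perform an EGD, if clinically indicated". But that footnote covers discontinuation for any reason, so the tension applies to all early terminators. Section 4.1.6.2 takes Week 26 non-responders from Week 28 straight to follow-up without naming an Early Termination Visit. The point made here does not rest on that footnote, and the change proposed here would not settle it.

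Finally, SAP Sections 3.1 and 16.2.2 have these subjects leaving at Week 26. If dosing ended then, the gap would be 14 days. The protocol says Week 28 throughout, however, and the SAP does not govern EGD or visit timing. Nor does the SAP wording alter a result: these subjects count as non-responders at Week 52 either way.

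**Conclusion.** The date conflict holds. For a Week 26 histologic non-responder who stops drug at Week 28 and has Follow-up 14 days after the last dose, the scheduled EGD misses the 3-week limit by 7 days nominally, and by 3 to 11 days within the stated windows. The consequence is an unscheduled repeat endoscopy or a protocol deviation.

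It is a minor operational and patient-burden issue. A reader might infer harm to the efficacy results, and the documents do not support that: the Week 12 primary endpoint and the Week 26 response classification are both fixed before the conflict arises.

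The verdict rests on a 14-day Follow-up with no window, and on the absence of an EGD at Week 28, which Table 4-2 shows clearly. The columns of Table 4-3 are disordered in the copy reviewed. That no EGD is marked at Follow-up is therefore inferred by lining its EGD row up with neighbouring rows.

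No count of affected subjects is claimed. Section 2.5 already reports the interim analysis, which SAP Section 4 places after all randomized subjects have completed Week 12, so many of those concerned may already have passed Week 28. No date conflict is claimed for Week 52 completers or for other early terminators.

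**What to change.** Add one sentence to Section 4.1.8 and to the Follow-up Visit paragraph of the Synopsis: *For Week 26 histologic non-responders who stop treatment at Week 28, the Week 26 EGD is the final EGD and the 3-week limit does not apply.* Leave the requirement as it is for everyone else.

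If all such subjects have already left the study, issue the sentence as a clarification, so that the absence of a second EGD is not logged as a deviation.

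The cost is one sentence in two places. No visit or scheduled EGD is added or removed, no endpoint data are lost, and the SAP needs no change for this point.
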